## 3 STUDY DESIGN

### 3.1 *Randomization Methodology*

Randomization will be accomplished by means of a web-based randomization system and will be stratified by center. The program used is Medidata Rave RTSM. The randomization schedule is generated by an unblinded statistician per the protocol requirements and loaded in the system.

The randomization sequence will be generated by random computerized sequence in blocks of 4.

### 3.2 *Blinding*

The treatment assignment is double-blinded and will not be known by the patients, the physician and clinical staff involved in the patient care.

The preparation and/or administration of the products will be done by designated personnel that are not involved in any other aspects of the trial.

The study blind will be broken on completion of the clinical study and after the study database has been locked.

The randomization code must not be broken except in emergency situations where the identification of a subject's study treatment is required by an investigator for further treatment of the patient. Randomization information will be held by designated individual(s). The date and reason for breaking the blind must be recorded.

## 4 STUDY OBJECTIVES AND ENDPOINTS

### 4.1 *Efficacy*

#### 4.1.1 Primary Efficacy Objective

As stated in section 4.1.1 of the study protocol, the primary objective for efficacy of the CARDIOL 100-03 study is to evaluate the effect of CardiolRx™ on prevention of cardiovascular (CV) and COVID-19 complications in patients hospitalized for COVID-19.

#### 4.1.2 Primary Efficacy Outcome

The primary composite endpoint in this study is to experience one of the following events during the first 28 days post randomization:

- All-cause mortality
- Requirement for intensive care unit (ICU) admission and/or ventilatory support due to COVID-19
- CV complications\*:
  - heart failure (HF) or
  - acute myocardial infarction (AMI) or
  - Myocarditis or
  - new sustained or symptomatic arrhythmia or
  - stroke

\*Outcome definitions can be found in Appendix 17.8 of the study protocol.

#### 4.1.3 Secondary Efficacy Objectives

Secondary objectives include the improvement in other clinical parameters during 28 days post randomization.

#### 4.1.4 Secondary Efficacy Parameters

Secondary efficacy parameters include:

-Win Ratio of Ordinal Outcome Scale endpoint:

- 1) not hospitalized and no limitations of activities
- 2) not hospitalized, with limitation of activities, home oxygen requirement, or both;

- 3) hospitalized, not requiring supplemental oxygen and no longer requiring ongoing medical care
- 4) hospitalized, not requiring supplemental oxygen but requiring ongoing medical care
- 5) hospitalized, requiring any supplemental oxygen;
- 6) hospitalized, requiring noninvasive ventilation or use of high-flow oxygen devices;
- 7) hospitalized, receiving invasive mechanical ventilation or extracorporeal membrane oxygenation (ECMO);
- 8) MI or stroke diagnosed since randomization
- 9) death.

- Change in high sensitivity-troponin (hs-troponin) from baseline to peak elevation during the 28-day treatment period
- Change in Tumor Necrosis Factor (TNF)-alpha from baseline to peak elevation during the 28-day treatment period

#### 4.1.5 Other Efficacy Parameters

Other efficacy parameters include:

- Percentage of patients developing any one of the primary endpoint components within 60 days post randomization
- CV mortality at 28 days post randomization
- Percentage of patients requiring dialysis within 28 days post randomization
- Win ratio of the Ordinal Outcome Scale endpoint within 60 days of randomization
- Patient Impression of Change Questionnaire (PICQ) at Day 28 and at Day 60
- Development of severe lymphopenia, defined as < 1000 cells/ microliter within 28 days post randomization
- Change in (elevation of) hs-troponin, NT-proBNP, D-dimer and in inflammatory markers (hs-CRP, ferritin, TNF-alpha, IL-1 beta, IL-6, IL-10) from baseline to Day 7 (AUC)
- Change from baseline to peak elevation of NT-proBNP, D-dimer and in inflammatory markers (hs-CRP, ferritin, IL-1 beta, IL-6, IL-10) during the 28-day treatment period
- Change from baseline to peak elevation of LDH during the 28-day treatment period
- Difference in cardiac magnetic resonance imaging (CMR) parameters: LVEF, LVEDV, LVESV, LAESV, ECV, GLS, LV mass, LGE extent and edema between the

---

two treatment groups after 4 weeks of study treatment (in a subset of patients at selected sites).

## **4.2 Safety**

### **4.2.1 Safety Objective**

The primary safety objective is to demonstrate that administration of CardiolRx™ in the proposed doses in this patient population is safe.

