- Patient Impression of Change Questionnaire (PICQ) at Day 28 and at Day 60
- Development of severe lymphopenia, defined as < 1000 cells/microliter within 28 days post randomization
- Change in (elevation of) hs-troponin, NT-proBNP, D-dimer and in inflammatory markers (hs-CRP, ferritin, TNF-alpha, IL-1 beta, IL-6, IL-10) from baseline to Day 7 [area under the curve (AUC)]
- Change from baseline to peak elevation of NT-proBNP, D-dimer and in inflammatory markers (hs-CRP, ferritin, TNF-alpha, IL-1 beta, IL-6, IL-10) during the 28-day treatment period
- Change from baseline to peak elevation of lactate dehydrogenase (LDH) during the 28-day treatment period
- Difference in cardiac magnetic resonance imaging (CMR) parameters between the two treatment groups after 4 weeks of study treatment (subset of patients at selected sites)

Primary Safety Objective

To evaluate the safety of CardiolRx™ in patients with COVID-19 infection

Primary Safety Endpoint

Number of serious adverse events (SAEs) and adverse events (AEs) during the 60-day study period in each group

Secondary Safety Endpoints:

Changes in C-SSRS, blood chemistry and hematology parameters (including lymphocyte count), ALT, AST, bilirubin, eGFR, creatinine, international normalized ratio (INR) as well as QTc interval

Number of Patients:

422 patients will be randomized (211 to CardiolRx™ and 211 to placebo)

Scheduled Duration of Study:

Estimated 9 months recruitment, 2 months follow-up, data cleaning 2 months and 2 months statistical analysis and reporting;

If all timelines are met, the total duration of the study will be approx. 15 months.

Design & Methodology

Multi-center, double-blind, randomized, placebo-controlled, parallel group design. 1:1 randomization.

Screening (Day 0-1): Patients hospitalized for COVID-19 will be screened. If patient consent can be obtained, baseline assessments will be carried out: Physical examination (including vital signs),

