11.2.3 Other Efficacy and Safety Analyses

The differences in continuous outcomes from baseline to 4 weeks post randomization between the two treatment groups will be analyzed using an ANCOVA. Treatment effect estimates and 95% confidence intervals will be determined.

Binary outcomes will be compared using Fisher's Exact test. The differences in proportions experiencing these outcomes will be estimated, along with 95% confidence intervals.

The elevation of hs-troponin, NT-proBNP, D-dimer and inflammatory markers over time from baseline to Day 7 will be compared using a ROC-AUC analysis, including data from all time points.

Win ratios for Ordinal Outcome Scale endpoint to 60 days after randomization will be analyzed as described above for the first secondary efficacy endpoint (Section 11.2.2).

Standard tests of the overall difference between treatment groups will be performed for the C-SSRS and the PICQ .

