11.7 Stopping Guidelines

The DSMC will evaluate the results of the interim analysis after approximately 50% of patients have completed the 28-Day assessment (or terminated the study early) with

PROPRIETARY AND CONFIDENTIAL

respect to prospectively defined criteria and make recommendations concerning safety concerns and the appropriateness of continuing the study.

Early stopping criteria:

The DSMC will recommend stopping the trial for safety reasons if there is a statistically significant imbalance of deaths in the active vs. the placebo group at a $p<0.05$ level, as determined by a two-sided Fisher's Exact test. In addition, the DSMC has the right to recommend stopping the trial early for evidence of harm that was not pre-defined by a formal stopping rule.

It is unlikely for the trial to stop early for overwhelming efficacy ($p<0.001$). Therefore, no stopping rule for superiority will be applied in order to collect sufficient data on secondary endpoints and evaluation of safety.

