### **4.2.2 Safety Endpoints**

The primary safety endpoint is the number of Serious Adverse Events (SAEs) and Adverse events (AEs) which occur during the 60-day study period.

The secondary safety endpoints include changes in C-SSRS, blood chemistry and hematology parameters (including lymphocyte count), ALT, AST, bilirubin, eGFR, creatinine, INR and QTc interval from Electrocardiogram (ECG) recordings at 5 hours post morning dose during 28 days post randomization.

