### 9.3.8 Adverse Events

Adverse events are to be recorded throughout the study, beginning at the moment of informed consent. AEs will be coded using MedDRA and displayed in tables and listings by System Organ Class (SOC) and Preferred Term (PT).

Analyses of adverse events will be performed for those events that are considered treatment-emergent, where a treatment-emergent AE (TEAE) is defined as one that started, or worsened in severity or seriousness following the first dose of IMP. An AE with onset prior to the start of the administration of the first dose of study drug, or where the stop date is before the start of the administration of the first dose of study drug, or where the study drug was not started, will be considered as pre-study. In case the onset date is on the same day as the first dose of study drug and either the time of first dose or time of AE onset is missing, then AE is considered treatment-emergent.

AE intensity will be qualified as mild, moderate, or severe. Maximum severity will be assumed for an AE with missing severity. The relationship to the study drug will be qualified as related (including categories related, probably, possibly) or unrelated.

If the AE start date is missing or partial, the AE will be assigned to the appropriate period using available start date information and the stop date, if present as described above.

The following tables will be presented for AEs incidence and/or number of events will be reported as appropriate:

- Overall summary of AEs
- TEAEs by system organ class and preferred term
- Treatment related TEAEs by system organ class and preferred term
- Serious TEAEs by system organ class and preferred term
- TEAEs by system organ class, preferred term and maximum severity
- TEAEs leading to study drug discontinuation by system organ class and preferred term
- Listing of AEs
- Listing of Serious TEAEs
- Listing of AESIs
- Listing of Deaths

Adverse event incidence is counted only once per system organ class and once per preferred term. The number and percent of subjects experiencing events are reported. Outputs reported at maximum severity show the highest severity reported by a patient per system organ class and preferred term.

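### The safety objective is to demonstrate that CardiolRx is safe, but no criterion for this is set and the SAP reports adverse events without a between-arm difference or interval

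*SAP*

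**What the plan says.** The protocol body and the SAP state the same safety objective in their sections 4.2.1: "The primary safety objective is to demonstrate that administration of CardiolRx™ in the proposed doses in this patient population is safe". The protocol synopsis is weaker: "To evaluate the safety of CardiolRx™ in patients with COVID-19 infection".

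The endpoint attached to the objective is a tally with no threshold. SAP 4.2.2 reads "The primary safety endpoint is the number of Serious Adverse Events (SAEs) and Adverse events (AEs) which occur during the 60-day study period", and Protocol 4.2.2 is equivalent.

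Protocol 11.2.3, which covers other efficacy and safety analyses, says "Binary outcomes will be compared using Fisher's Exact test" and continues "The differences in proportions experiencing these outcomes will be estimated, along with 95% confidence intervals". For continuous outcomes it plans ANCOVA, also with estimates and 95% intervals. Protocol 11.7 adds a stopping rule for an imbalance in deaths at the halfway interim analysis.

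The SAP was written after the trial had stopped early. Sections 6.2 and 6.4 remove all testing except for the bio- and inflammatory markers, section 6.3 drops the interim analysis, and section 10 says that summaries are descriptive. For adverse events, section 9.3.8 lists tables and listings and says "The number and percent of subjects experiencing events are reported". The SAP text mentions no between-arm difference and no interval for adverse events.

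**The concern.** A plan that sets out to demonstrate safety has to say what result would count: a margin, an upper bound on excess risk, or some other criterion. Without one, nobody can tell whether the objective was met. The SAP widens the gap. It keeps the confirmatory verb and reduces the adverse-event output to per-arm counts and percentages, which carry no measure of uncertainty about the comparison.

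What is at stake is how the safety results can be read. Two similar percentages from a small trial are compatible with no excess risk and also with a substantial one. An interval shows that range. A pair of percentages leaves the reader to work it out.

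**Working it through.** **Step 1: the passages side by side.**

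| Place | Aim or output for safety | Criterion or interval |
|---|---|---|
| Protocol synopsis | evaluate | none needed for that verb |
| Protocol 4.2.1, SAP 4.2.1 | demonstrate | none stated |
| Protocol 4.2.2, SAP 4.2.2 | number of SAEs and AEs over 60 days | none stated |
| Protocol 11.2.3 | Fisher's exact test and difference in proportions for binary outcomes | 95% interval, no margin |
| Protocol 11.7 | stop for an imbalance in deaths | a rule for detecting harm, not for establishing safety |
| SAP 9.3.8 | number and percent, listings | none stated |

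**Step 2: the one sized comparison.** The planned number is for efficacy: 19% against 9.5%, two-sided alpha 0.05, 80% power, 211 per group. The pooled formula is

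n = [1.960 × √(2 × 0.1425 × 0.8575) + 0.842 × √(0.19 × 0.81 + 0.095 × 0.905)]² / 0.095² = (0.969 + 0.412)² / 0.009025 ≈ 211.4.

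That is 212 after rounding up, which agrees with the stated 211. No sample size, margin or power is given for safety.

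**Step 3: what an interval would show.** The documents give no SAE rate and no sample size at termination. Assume equal true rates p of 10% or 20% in both arms, and take n = 211 per arm (planned) or n = 40 per arm (assumed). The approximate half-width of the 95% interval for the difference is 1.96 × √(2p(1−p)/n).

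- n = 211, p = 0.10: 1.96 × √(0.18/211) = 5.7 points
- n = 211, p = 0.20: 1.96 × √(0.32/211) = 7.6 points
- n = 40, p = 0.10: 1.96 × √(0.18/40) = 13.1 points
- n = 40, p = 0.20: 1.96 × √(0.32/40) = 17.5 points

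For example, 4 of 40 patients with an SAE in each arm would appear in the SAP table as 10.0% against 10.0%. The approximate interval for the difference would run from −13 to +13 points.

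**Step 4: what a real demonstration would need.** Purely as illustration, suppose the criterion were to exclude an excess of 5 points, with one-sided alpha 0.025, 80% power and equal true rates. Then n per arm = (1.960 + 0.842)² × 2p(1−p)/0.05².

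- p = 0.10: 7.849 × 0.18/0.0025, giving 566 per arm
- p = 0.20: 7.849 × 0.32/0.0025, giving 1005 per arm

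On these assumptions even the full planned trial could not have supported the verb for a margin of that size. With an assumed 10-point margin the numbers fall to 142 and 252, so the answer depends on a margin that neither document supplies.

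**The case against.** The best reply is that the SAP is open about what it does. It attributes the reduced reporting to early termination and calls its summaries descriptive. It carries the objective over from the protocol, whose synopsis already uses the milder verb. That is fair, and it makes this a mismatch of wording and output rather than a concealed claim. It does not remove the mismatch: the SAP says that it notes changes from the protocol, and it left the objective as it was.

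Three stronger readings are tempting, and the documents do not support them.

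- *An undetected difference will be taken as proof of safety.* No passage sets such a rule. The SAP runs no safety test, so it produces no non-significant safety result that could be misread.
- *The protocol offers only a significance test.* Section 11.2.3 also plans the difference with its interval, and intervals for continuous outcomes. The data safety and monitoring committee reviews SAEs by treatment code and QTc in the first 100 patients, and there is the stopping rule for deaths. None of these is a criterion for safety, but they are more than a test.
- *The low power of Fisher's test to detect harm shows the size of the problem.* That concerns a test the SAP no longer runs. Interval widths are the relevant measure.

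Two limits also stand. Section 11.2.3 refers to binary outcomes and does not name adverse-event incidence, and the primary safety endpoint can be read as a count of events. So it is not certain that the protocol's interval was meant for these rows. And the statement about SAP output rests on the SAP's text; pages after its reference list were not available.

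**Conclusion.** The point holds as a mismatch between objective and analysis. Two sections set out to demonstrate safety, the synopsis to evaluate it, no criterion is given anywhere, and the SAP text provides no between-arm estimate for adverse events. The stated objective cannot be met by the stated analysis.

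The argument that testing was dropped because of early termination does not cover the interval. An interval is estimation and needs no test, and SAP 9.2 still plans between-arm ANCOVA for the markers.

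The size is illustrative only: about 6 to 8 points either side at 211 per arm and 13 to 18 points at 40 per arm. It rests on assumed equal SAE rates of 10% to 20%, an assumed reduced size, and a normal approximation. It does not follow that the drug is unsafe, or that the sponsor intends to claim safety from similar percentages.

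**What to change.** 1. In Protocol 4.2.1 and SAP 4.2.1, replace the aim of demonstrating that the drug is safe with the synopsis aim of evaluating its safety. Record the change in SAP section 10.
2. In SAP 9.3.8, add the CardiolRx minus placebo difference in the proportion of patients, with a two-sided 95% confidence interval, for any treatment-emergent AE (TEAE), any serious TEAE, TEAE leading to study drug discontinuation, and death. Present it as estimation, with no p-value. Name an interval method that behaves well with few or no events, because the approximation used above does not.

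The cost is a wording change in two places and one extra column in the tables. The intervals will be wide and the safety statement more modest, which reflects what the data can show. No new data are needed and no patient care is affected.

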### **4.2.2 Safety Endpoints**

The primary safety endpoint is the number of Serious Adverse Events (SAEs) and Adverse events (AEs) which occur during the 60-day study period.

The secondary safety endpoints include changes in C-SSRS, blood chemistry and hematology parameters (including lymphocyte count), ALT, AST, bilirubin, eGFR, creatinine, INR and QTc interval from Electrocardiogram (ECG) recordings at 5 hours post morning dose during 28 days post randomization.

## **4.3 Centralized Assessment of Endpoints**

The Clinical Endpoint Adjudication Committee (CEC) will consist of at least three clinicians appointed by the Steering Committee. The CEC will classify all SAEs using pre-specified definitions described in the Event Classification manual, based on medical records and other documents. In addition, all endpoints will be verified by the CEC.

## 5 DEFINITION OF ANALYSIS POPULATIONS

The following analysis populations will be defined for this trial.

### ***5.1 Intention-to-treat population (ITT)***

The primary analyses will be performed on the ITT population. All patients who were randomized will be included in the ITT analyses.

### ***5.2 Safety population (SAF)***

The Safety Population (SAF) includes all subjects who received any study drug.

### ***5.3 Per- protocol population (PPP)***

The protocol defined a per-protocol population. However, due to the early termination of the study the PPP will not be generated.

### ***5.4 Protocol Deviations***

The sponsor, or designee, will be responsible for producing the final protocol deviation/violation file (formatted as an Excel file or SAS dataset). This file will be finalized prior to hard database lock. Protocol deviations will be reported in a data listing for all subjects in the ITT population.

## 6 STATISTICAL METHODS

### 6.1 Sample Size Justification

Assuming that 19% of patients qualifying for the study in the placebo group would develop one or more primary outcomes, a treatment effect of lowering the event rate by 50% (i.e. only 9.5% of patients treated with CardiolRx™ would experience a primary outcome event, a two-sided alpha of 0.05 and 80% power, 211 patients per group (422 in total) would be required.

The protocol contained information to consider an adjustment to the sample size. Due to the early termination of the study no sample size re-estimation will be performed.

### 6.2 General Statistical Methods and Data Handling

Tabulations will be produced for appropriate demographic, baseline, efficacy, and safety parameters.

Due to the early termination of the study no statistical testing will be performed, with the exception of the bio- and inflammatory marker data (see Section 9). All summaries will be presented descriptively.

Listings will be sorted by treatment and subject ID unless specified otherwise.

#### 6.2.1 Computing Environment

All analyses will be performed using SAS statistical software (Version 9.4 or later), unless otherwise noted. Medical history and adverse events will be coded using the Medical Dictionary for Regulatory Activities (MedDRA). Medications will be coded using the World Health Organization (WHO) Drug dictionary. Versions of dictionaries will be indicated in the relevant tables and listings.

#### 6.2.2 Continuous Variables

For continuous variables, the mean, median, standard deviation (SD), first and third quartiles (Q1 and Q3), and minimum and maximum values will be presented. Means, medians and percentiles will be displayed to one more decimal place than the data, dispersion statistics (e.g., standard deviation) will have two more decimal places, and the minimum and maximum will be displayed to the same number of decimal places as reported in the raw data.

#### 6.2.3 Categorical Variables

Categorical variables will be summarized by presenting the frequency and percent. Percentages will be based on the number of subjects in the column header unless otherwise specified in the footnote. For each variable, all categories will be shown. Zero

frequencies (but not the percent) within a category will be presented. Percentages will be displayed with one decimal place

### **6.3 *Interim Analysis***

The protocol contained information to describe a formal interim analysis of the primary endpoint. Due to the early termination of the study no interim analysis will be performed.

### **6.4 *Statistical Inference***

Due to the early termination of the study no statistical testing will be performed, with the exception of the bio- and inflammatory marker data (see Section 9). All summaries will be presented descriptively.

